6.6.4 Concomitant Medications

Concomitant medications will be listed by patient.

6.6.5 Deaths

The number of total deaths, deaths that occur within 30 days of last study treatment, and deaths that occur more than 30 days after last study treatment as well as the relationship to disease will be summarized by dose level and total. In addition, cause of death will be identified by descending MedDRA preferred term (unless otherwise specified) and summarized by dose level and total. Death information will be listed by patient.

6.6.6 ECOG Performance Status

Shifts from baseline to the best and worst post-baseline score will be tabulated.

6.7 Pharmacokinetics and Immunogenicity Endpoints

6.7.1 Pharmacokinetics

PK concentration will be summarized with descriptive statistics or plotted at each PK sampling time point using the All Treated Patients analysis set. The following PK parameters will be determined where data allow and will be summarized using All Treated Patients analysis set.

- Area under the curve (AUC)
- Concentration at the end of infusion (C_{eot}) or maximum observed concentration (C_{max})
- Trough concentration (C_{trough})
- Terminal or apparent terminal half-life ($t_{1/2}$)
- Systemic clearance and volume of distribution at steady state

- Accumulation ratio

6.7.2 Antitherapeutic Antibody (ATA) Incidence Rate

The ATA incidence rate is defined as the proportion of patients that develop ATA at any time during the study.

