2. OBJECTIVES

This study will evaluate the safety and antitumor activity of SEA-BCMA as monotherapy and in combination in subjects with RRMM. Specific objectives and corresponding endpoints are detailed in [Table 1](#).

Table 1: Objectives and corresponding endpoints

Primary Objectives	Corresponding Primary Endpoint
Evaluate the safety and tolerability of SEA-BCMA monotherapy in subjects with relapsed or refractory multiple myeloma (RRMM) Identify the maximum tolerated dose (MTD) and/or optimal dose and schedule of SEA-BCMA monotherapy, and in combination with dexamethasone, in subjects with RRMM	Type, incidence, severity, seriousness, and relatedness of adverse events (AEs) Type, incidence, and severity of laboratory abnormalities Incidence of dose-limiting toxicities (DLTs)
Evaluate the safety and tolerability of SEA-BCMA in combination with SOC therapies in subjects with RRMM	
Secondary Objectives	Corresponding Secondary Endpoints
Identify a recommended single-agent dose and schedule of SEA-BCMA Assess the pharmacokinetics (PKs) of SEA-BCMA Assess the immunogenicity of SEA-BCMA Assess the antitumor activity of SEA-BCMA	Incidence of DLTs, cumulative safety and activity by dose level and schedule Maximum serum concentration and area under the serum concentration-time curve Incidence of SEA-BCMA antitherapeutic antibodies (ATA) Best response per the International Myeloma Working Group (IMWG) uniform response criteria (Kumar 2016) Objective response rate (ORR) Duration of objective response (OR) and complete response (CR) Progression-free survival (PFS) Overall survival (OS)
Exploratory Objectives	Corresponding Exploratory Endpoints
Assess incidence and level of BCMA expression in RRMM and relationship to clinical response to SEA-BCMA Assess the pharmacodynamic effects and biomarkers of response, toxicity, and resistance to SEA-BCMA Assess minimal residual disease (MRD) in subjects with very good partial response (VGPR) or better Assess impact of SEA-BCMA in combination with SOC therapies on health-related quality of life (HRQoL) from the subject's perspective.	Characterization of BCMA expression on malignant plasma cells Exploratory biomarkers of SEA-BCMA mediated pharmacodynamic effects Rate of MRD clearance Descriptive outcomes of qualitative interviews Maximum serum concentration and area under the serum concentration-time curve

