6.9. Infusion/Hypersensitivity Reaction Follow-up Visit (24 to 72 hours; Part A only)

For subjects in Part A, the IHR Follow-up visit is scheduled 24-72 hours after the initial IHR visit, and the following assessments are performed:

- Physical exam

- Vital signs
- Blood and urine samples by local laboratory
 - CBC with differential
 - Serum chemistry panel
 - Urinalysis (microscopy required if urinalysis results are abnormal)
- Blood sample collection for PK/biomarkers assessment by central laboratory ([Appendix B](#))

Timing of the IHR Follow-up visit blood draw may overlap with another protocol-defined blood draw. If this occurs, collect blood samples for the IHR Follow-up visit local and central labs as required; lab tests for the protocol-defined blood draw do not need to be duplicated if they are collected as part of the IHR Follow-up visit.

6.10. End of Treatment Visit (30 to 37 days after last dose of study drug)

EOT visits should occur 30 to 37 days after the last dose of study drug unless delayed due to an AE. Note: EOT evaluations must be performed before initiation of a new therapy. If EOT evaluations are completed before 30 days after the last study treatment, the subject will be contacted 30 to 37 days following the last treatment to assess for AEs.

- ECG in triplicate
- Physical examination
- ECOG performance status
- Vital signs
- Weight
- Pregnancy test for subjects of childbearing potential
- Blood and urine samples for local laboratory assessment
 - CBC with differential
 - Serum chemistry panel
 - Urinalysis (microscopy required if urinalysis results are abnormal)
 - UPCR calculation via spot urine test (only required if not conducted within 4 weeks prior to EOT)
- Response assessments by local laboratory
 - SFLC
 - BM aspirate and biopsy, if collected per SOC, or to confirm CR, to be submitted for central assessment of markers of drug activity and resistance to SEA-BCMA
 - SPEP/immunofixation
 - UPEP/immunofixation

- In cases of suspected or known plasmacytoma, plasmacytoma evaluation, per institutional standard imaging modality, should be performed every 4 cycles or to confirm a response of PR or better, or as clinically indicated to confirm PD.
- Quantitative immunoglobulins
- Blood sample for Modified SPEP for subjects with IgG myeloma only
- Blood samples for PK/ATA/biomarkers assessments by central laboratory ([Appendix B](#))

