9.3.6. Pharmacokinetic and Immunogenicity Analyses

The PK of SEA-BCMA will be evaluated by noncompartmental analysis. The following PK parameters will be determined where data allow:

- Area under the curve
- Concentration at the end of infusion (C_{eoI}) or C_{max}
- Trough concentration (C_{trough})
- Terminal or apparent terminal half-life ($t_{1/2}$)
- Systemic clearance and volume of distribution at steady state

- Accumulation ratio

The incidence of ATA will be summarized by descriptive statistics.

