Cycle 4 and subsequent cycles	1	Predose	Within 4 hr prior to dose	START of infusion, 1 st dose	X	X ^C			X	X	X ^K	X	X				
		End of study drug administration	Within 15 min post IV infusion	END of infusion, 1 st dose	X												
	15	Predose	Within 4 hr prior to dose	START of infusion, 2 nd dose	X												
		End of study drug administration	Within 15 min post IV infusion	END of infusion, 2 nd dose	X												

Cycle	Study day	Time	Window	Relative Time	Peripheral Blood ^A										Bone Marrow ^A			
					SEA-BCMA PK	SEA-BCMA ATA	Genotyping	Immunophenotyping	Plasma cytokines/chemokines	Soluble target and ligands	Plasma Biomarkers	PBMCs	SFLC	Modified SPEP ^L	Immunophenotyping (including BCMA characterization)	Gene expression/NGS/FISH	MRD	BM plasma
	22	168 hr	±24 hr	START of infusion, 2 nd dose					X				X		X			
				IHR visit	NA	X	X						X					
				IHR follow-up visit	NA	X	X			X			X					
				At time of CR assessment	NA				X ^J	X ^J	X	X ^J			X ^J	X	X	X ^J
				EOT	NA	X	X		X ^J	X	X	X	X	X	X ^{I,J}	X ^I	X ^I	X ^{I,J}
				Follow-up	NA									X ^Q	X ^{I,Q}	X ^{I,Q}	X ^{I,Q}	X ^{I,Q}

ATA = antitherapeutic antibody; BCMA = B-cell maturation antigen; BM = bone marrow; CR = complete response; EOT = end of treatment; FISH = fluorescent in situ hybridization; IHR = infusion/hypersensitivity reaction; IV = intravenous; MRD = minimal residual disease; NA = not applicable; NGS = next generation sequencing; PBMC = peripheral blood mononuclear cell; PK = pharmacokinetic; SFLC = serum free light chain; SPEP = serum protein electrophoresis

- A Blood and bone marrow aspirate and biopsy to be collected for central analysis. Analysis may include BCMA characterization (flow cytometry, gene expression, and immunohistochemistry), risk stratification (gene expression profiling, phenotypic profiling), and NGS analysis (including MRD determination).
- B Sample obtained only for subjects not starting the next dose on Day 15 or 29 [± 72 h] and not in EOT visit
- C Required in first 5 cycles and every fifth cycle thereafter
- D Cycle 1 only
- E Cycle 1 and 2 only
- F End of Cycle 2 only (Day 22 to 28)
- G Cycle 1 Day 1 predose window is within 1 day of Day 1
- H Labs may be drawn at the site or, except for Cycle 1, may be drawn by a home healthcare provider

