4.1 All Treated Patients Analysis Set

The All Treated Patients set includes all patients who receive any amount of SEA-BCMA. The All Treated Patients set will be used for presentation of safety data and efficacy endpoints.

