5.6 Handling of Dropouts and Missing Data

With the exception of the scenarios covered in this section, missing data will not be imputed.

AE dates will be imputed for the purpose of calculating duration of events and treatment-emergent status (see [Appendix A](#) for imputation details). Censoring will be described in Section 6 with each planned analysis, as applicable.

Unless otherwise specified, lab values which are recorded or provided as being less than the lower limit of quantification (LLOQ), will be included in figures and summaries as LLOQ. For the purpose of grading, lab values reported as less than LLOQ will be imputed as LLOQ.

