6.5.1.5 Overall Survival (OS)

Overall survival is defined as the time from the start of study treatment to date of death due to any cause. Specifically,

$$\text{OS} = \text{Date of death} - \text{Date of first study treatment} + 1.$$

In the absence of confirmation of death, OS will be censored at the last date the patient is known to be alive. If the last recorded date where a patient is known to be alive is the date of first dose of study treatment, survival time will be censored on the treatment start date (i.e., OS duration of 1 day).

Overall survival will be analyzed using Kaplan-Meier methodology and Kaplan-Meier plots will be provided. The median OS and its two-sided 95% confidence intervals (CI) will be calculated using the complementary log-log transformation method (Collett 1994).

ATA incidence will be summarized by dose level and total for all treated patients.

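### ATA incidence is reported over all treated patients, so those with no post-baseline ATA result lower it relative to the rate among tested patients, by an amount the documents do not give

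*SAP*

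**What the plan says.** Incidence of ATA is the only endpoint listed for the secondary immunogenicity objective (Protocol Section 2 and SAP Section 2, Table 1 in each).

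- **Numerator.** SAP 6.7.2: "The ATA incidence rate is defined as the proportion of patients that develop ATA at any time during the study". This sentence names no denominator.
- **Denominator.** It is in the last line of SAP 6.5.1.5, under overall survival: "ATA incidence will be summarized by dose level and total for all treated patients". SAP 4.1 defines that set: "The All Treated Patients set includes all patients who receive any amount of SEA-BCMA". No ATA sample is required.
- **Protocol analysis text.** Protocol 9.3.6 adds only this: "The incidence of ATA will be summarized by descriptive statistics".
- **Sampling.** Appendix B schedules ATA predose on Day 1, with the footnote "Required in first 5 cycles and every fifth cycle thereafter". The EOT visit (Protocol 6.10, 30 to 37 days after the last dose) lists "Blood samples for PK/ATA/biomarkers assessments by central laboratory". In Part A, the Appendix B rows for the infusion-reaction visit and its follow-up also appear to mark an ATA sample. The long-term follow-up list in Protocol 6.11 has none.
- **Missing data.** SAP 5.6: "With the exception of the scenarios covered in this section, missing data will not be imputed". The listed exceptions concern adverse event dates and laboratory values below the quantification limit; ATA is not among them.

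Neither document defines an ATA-evaluable set or says how to treat a patient with no post-baseline result or with a positive baseline result.

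**The concern.** A patient can be observed to develop ATA only if a sample taken after dosing has been tested. The first such sample on the regular schedule is Cycle 2 Day 1, about four weeks after the first dose. Someone who leaves during Cycle 1 and has no EOT sample (nor, in Part A, an infusion-reaction sample) contributes one to the denominator and can contribute nothing to the numerator.

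The SAP allows for such patients. Section 5.5 has a rule for when no EOT visit takes place, and a response rule for subjects who stop without further treatment after Cycle 1.

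The immunogenicity summary is at stake. A reader would see a proportion without knowing how many patients had been tested, and results are shown by dose level, where one untested patient can matter. For response, counting unevaluable patients as failures is conservative. For immunogenicity, the same all-treated default makes the drug look better than the tested patients alone would.

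The second gap is the word *develop*. A Cycle 1 predose sample is scheduled, so baseline positivity can be known, but the SAP does not say whether a baseline-positive patient is counted.

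**Working it through.** **Inputs.** The documents give no expected ATA rate, no expected share of untested patients and no ATA sample size, so there is no plan figure to reproduce. Both p and m below are assumptions. The group sizes are from the documents: cohorts of at most 4 in escalation, expansion cohorts of up to 20, and 131 in total.

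**Formula.** Let p be the ATA rate among tested patients and m the fraction of treated patients with no post-baseline result.

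- Reported all-treated rate = p(1 − m)
- Shortfall against the tested-patient rate = p − p(1 − m) = pm

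The shortfall is zero only if m = 0 or p = 0.

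**Numbers at p = 20%.**

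| m (assumed) | Reported rate | Shortfall, points |
|---|---|---|
| 5% | 0.20 × 0.95 = 19.0% | 1.0 |
| 10% | 0.20 × 0.90 = 18.0% | 2.0 |
| 20% | 0.20 × 0.80 = 16.0% | 4.0 |

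Over p and m each from 5% to 30%, the shortfall runs from 0.05 × 0.05 = 0.25 points to 0.30 × 0.30 = 9.0 points.

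**In whole patients (illustrative counts).**

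| Group | Untested | Positive | All treated | Tested only |
|---|---|---|---|---|
| 4 | 1 | 1 | 1/4 = 25.0% | 1/3 = 33.3% |
| 20 | 2 | 4 | 4/20 = 20.0% (95% CI 5.7–43.7%) | 4/18 = 22.2% (6.4–47.6%) |
| 20 | 4 | 3 | 3/20 = 15.0% (3.2–37.9%) | 3/16 = 18.8% (4.0–45.6%) |
| 131 | 13 | 24 | 24/131 = 18.3% (12.1–26.0%) | 24/118 = 20.3% (13.5–28.7%) |

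The intervals are exact Clopper-Pearson. The 4-patient row corresponds to m = 25%, outside the 5% to 20% range, because one patient is the smallest possible loss in a group that size.

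**Against the true rate in all treated patients.** Let q be the unobserved rate among untested patients. The true rate is p(1 − m) + qm.

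- The all-treated figure falls short of the truth by qm: zero if q = 0, and pm if q = p.
- The tested-only figure exceeds the truth by (p − q)m: pm if q = 0, and zero if q = p.

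At p = 20% and m = 10%, with q between 0 and p, each figure is off by between 0 and 2.0 points, and where one is exact the other is furthest away.

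**Baseline-positive patients.** Take the group of 20 with 2 untested and 4 new positives, and suppose one more tested patient was positive at baseline. Counting that patient gives 5/20 = 25.0%, above the treatment-emergent figure of 4/18 = 22.2%. The two gaps can therefore work in opposite directions.

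**The case against.** The strongest reply is that the documents nowhere say untested patients are negative. Where the SAP wants unevaluable patients counted as failures it says so, as for objective response in 6.5.1.1; for complete response in 6.5.1.2 it scores them as not evaluable. SAP 6.7.1 also names the All Treated set for PK parameters that are determined only where data allow, so naming a set could be a population label. This does not remove the point. A proportion needs a denominator, the SAP names one, and the ATA sentence carries no qualifier about available data. If a tested-only denominator was intended, the same sentence needs changing.

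A reader might infer that the rate is always biased low. The documents do not support that. Counting baseline-positive patients would raise it. And if patients who left within about four weeks had no time to develop antibody, the all-treated proportion is right for all treated patients and the tested-only rate is slightly high. A low rate is certain only relative to the rate among tested patients, for a given rule on who counts as positive.

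The reply is also right that the affected group is limited. The EOT sample, the possible Part A infusion-reaction samples and the eligibility requirement of more than 3 months' life expectancy all reduce it. The shifts in the 20-patient examples are small beside the width of the intervals. On baseline positivity, *develop* most naturally means new onset, so that gap is one of wording.

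**Conclusion.** The point holds in a limited form. With SAP 6.5.1.5 and 6.7.2 read together, treated patients without a post-baseline ATA result are in the denominator and cannot be in the numerator, so the reported incidence is p(1 − m), below the rate among tested patients whenever m and p exceed zero. On the assumptions of p = 20% and m = 5% to 20%, that is 19% to 16%, a shift of 1 to 4 points. Small dose-level groups can shift more.

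The documents supply neither p nor m, so the actual size is unknown. The distance from the true rate in all treated patients also depends on what would have been found in those untested. The treatment of baseline-positive patients is a separate ambiguity that could act upwards. The analyses are descriptive, and no test, sample size or dose-finding rule in the plan uses ATA incidence, so this is a minor correction.

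**What to change.** In SAP 6.7.2, and in the ATA sentence now at the end of 6.5.1.5 (which would sit better in 6.7.2):

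1. Use as denominator the treated patients with at least one post-baseline ATA result.
2. Report, by dose level and in total, the number of treated patients without one.
3. Count treatment-emergent ATA: baseline negative or missing, then positive after dosing.
4. Show baseline-positive patients separately.
5. Keep the all-treated proportion as a supplementary figure if wanted.

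The cost is one definition and a few table rows; no new data are needed. SAP Section 1 allows the change by amendment before database lock or by documenting it in the clinical study report. The small downside is that, if early leavers truly had no time to develop ATA, the new rate is slightly higher than the all-treated rate. Showing the number untested beside it lets the reader judge.

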7 INTERIM ANALYSIS

No other formal statistical interim analyses are planned. Data will be evaluated after each dose level to determine DLTs and inform dose-escalation decisions. The SMC will monitor the trial for safety and DLTs on an ongoing basis. The process for SMC decisions and the roles and responsibilities of the SMC will be detailed in a separate document.

8 CHANGES FROM PLANNED ANALYSES

8.1 Changes from the Original Protocol

Efficacy-Evaluable Analysis Set was not used in the final CSR analysis.

8.2 Changes from the Original SAP

Efficacy-Evaluable Analysis Set, PK Analysis set were not used in the final CSR analysis.

The following Subgroups will not be explored.

- Cytogenetic risk group (high, intermediate, normal)
- Refractory to prior therapies (refractory to IMiD and PI vs not; refractory to IMiD and PI and anti-CD38 antibody vs not)
- Number of prior therapies (<5 vs \geq 5)
- Baseline beta-2 microglobulin (<3.5 vs \geq 3.5)
- ISS stage at initial diagnosis (1, 2, 3)
- MRD-negative CR rate and its exact two-sided 95% confidence interval will also be presented.

MRD negative CR, and duration of CR is not summarized.

Exploratory analyses which will be covered by Biomarker Analysis Plan are removed.

IRR by cycle analysis is removed.

ECG summary analysis is removed.

REFERENCES

Clopper CJ and Pearson ES (1934). The use of confidence or fiducial limits illustrated in the case of the binomial. *Biometrika* 26: 404-413.

Collett D (1991). Statistical inference for binary data. *Modelling Binary Data*. London, Chapman and Hall: 23-26.

Collett D (1994). Interval-censored survival data. *Modelling survival data in medical research*. Boca Raton, Fla., Chapman & Hall/CRC: 237-251.

Appendix A Imputation of Partially Unknown Adverse Event Dates

For an adverse event (AE) with a partial start or end date, if it can be determined that the event occurred prior to the first dose of any study treatment, the partial date will not be imputed; otherwise, the AE partial date will be imputed using the rules described below.

- a **A. AE occurred prior to the first dose of any study treatment**, i.e., satisfies either i or ii below:
 - i. Onset date is prior to the first dose date
 - ii. (Onset date is completely missing or the same as the first dose date) and (Onset Period is "started before the signing of consent" or "started after consent but before the first dose of any study treatment")
- 5. **B. AE occurred after the first dose of any study treatment**, i.e., satisfies either i or ii below:
 - i. Onset date is after the first dose date
 - ii. (Onset date is completely missing or the same as the first dose date) and (Onset Period is "started after first dose of any study treatment" or missing)
- b Note: compare AE onset date with the first dose date on the common precision only for all the date comparisons described in A and B above; e.g., "2019" is considered greater than "2018-xx-xx"; "2019-03" is considered equal to "2019-03-xx". Issue a WARNING to the log when (onset date is completely missing or the same as the first dose date) and Onset Period is missing.

For AE occurred after the first dose of any study treatment (see B. above) only:

- Impute incomplete AE start date as the followings:
 - ❖ AE day only is missing: if the month/year is the same as the month/year of first dose of any study treatment, AE start date will be imputed as the first dose date of any study treatment; if the month/year is after the month/year of first dose of any study treatment, AE start date will be imputed as the first day of the month
 - ❖ AE day and month are missing, or month only is missing: if the year is the same as the year of first dose of any study treatment, AE start date will be imputed as the first dose date of any study treatment; if the year is after the year of first dose of any study treatment, AE start date will be imputed as January 1st
 - ❖ AE day, month and year are missing, or year only is missing: AE start date will be imputed as the first dose date of any study treatment
- Impute incomplete AE end date as the followings when AE outcome is "recovering/resolving", "recovered/resolved", "recovered/resolved with sequelae", or "fatal":
 - ❖ AE day only is missing: AE end date will be imputed as the minimum of (last day of the AE end date month/year, death date, data extraction date, EOS date)
 - ❖ AE day and month are missing, or month only is missing: if the year is equal to the year of the last dose date, AE end date will be imputed as the minimum of (December 31st of the AE end date year, last dose date + 30, death date, data extraction date, EOS date); if the year is not equal to the year of the last dose date, AE end date will be imputed as the minimum of (December 31st of the AE end date year, death date, data extraction date, EOS date)
 - ❖ AE day, month and year are missing, or year only is missing: AE condition end date will not be imputed

NOTE: if the subject did not receive any dose of the study treatment, do not impute any AE of the subject

Signature Page for SGN-CLIN-026821 v1.0

eSignature Approval	PPD
	Biostatistics
	25-Aug-2023 19:03:55 GMT+0000

eSignature Approval	PPD
	Clinical Development
	25-Aug-2023 19:41:24 GMT+0000

eSignature Approval	PPD
	Biostatistics
	30-Aug-2023 17:37:11 GMT+0000

Signature Page for SGN-CLIN-026821 v1.0
